# **Study Design**

This will be a single arm, open-label phase I study. Patients will receive 1500mg of lapatinib administered daily for at least 9 days.

Prior to entering the study the ErbB2 status will be required for each patient. Only patients with treatment-naïve, ErbB2 positive, as defined by either overexpression of ErbB2 (3+) by semi-quantitative IHC or amplification of the ErbB2 gene by fluorescence in situ hybridization (FISH), breast tumors measuring 1 cm or greater will be eligible for the study. For eligible patients, the archived tumor tissue obtained at diagnosis will represent the pre-treatment biopsy and be required for entry into the study. The pre-treatment biopsy tissue will be examined using technologies for measuring biomarkers involved in regulating tumor cell proliferation and survival (e.g., ErbB2, ERK1/2, AKT, and other downstream pathways regulated by ErbB receptor signaling). Patients will receive treatment with lapatinib for a minimum of 9 days prior to surgical resection. Patients will have their post-treatment surgical resection performed within 24 hours of last lapatinib dose. Tumor tissue obtained at resection will be examined for biomarkers as described above and compared with the results from the pre-treatment biopsy. In addition, tumor obtained at the time of resection will be examined for steady state, trough concentrations of lapatinib.

Safety (AEs, clinical laboratory values) will be assessed throughout the study.

# **Study Population**

Approximately 20 evaluable patients will be enrolled from approximately 16 study centers. Female patients, aged 18 years or older with a breast tumor measuring 1 cm or greater with evidence of ErbB2 protein overexpression as measured by IHC 3+ or ErbB2 gene amplification as measured by FISH and who will receive adjuvant chemotherapy, hormonal therapy or radiation therapy will be enrolled. Patients must be naïve to cytotoxic, radiation, hormonal and biologic therapy to treat this incidence of breast cancer.

In addition to the criteria above, a patient will be eligible for inclusion only if all of the following criteria apply:

- a. Non-child-bearing potential (i.e. physiologically incapable of becoming pregnant), including any female who:
  - Has had a hysterectomy
  - Has had a bilateral oophrectomy (ovariectomy)
  - Has had a bilateral tubal ligation, or
  - Is post-menopausal (a demonstration of total cessation of menses for  $\geq 1$  year)
- b. Childbearing potential, has a negative serum pregnancy test at Screening and agrees to one of the following where considered acceptable by the institution IEC or IRB:
  - Complete abstinence form sexual intercourse from 2 weeks prior to administration of the study drug, throughout the active study treatment period, and through the follow-up visit (to occur 28 days after last dose of study medication).

- Barrier contraception (condom with spermicidal jelly, foam suppository, or film; diaphragm with spermicide; or male condom and diaphragm).
- Male partner who is sterile prior to the female subject's entry and is the sole sexual partner for that female subject.
- Implants of levonorgesterol.
- Injectable progestogen.
- Any intrauterine device (IUD) with a documented failure rate of less than 1% per year.
- Oral contraceptives (either combined or progetogen only).
- c. Karnofsky Performance Status (KPS)  $\geq 70$  (Appendix 4)
- d. Ability to swallow and retain oral medication.
- e. Provided written informed consent.
- f. Hemoglobin  $\geq 9$  gm/dL.
- g. Absolute granulocyte count  $\geq 1,500/\text{mm}^3$  (1.5 x  $10^9/\text{L}$ ).
- h. Platelet count  $\geq 100,000/\text{mm}^3 (100 \times 10^9/\text{L})$ .
- i. Serum creatinine  $\leq 3 \text{ mg/dL}$ .
- j. Total bilirubin  $\leq 1.5 \text{mg/dL}$ .
- k. Aspartate and alanine transferase (AST & ALT)  $\leq$  3 times the upper limit of the reference range.

# **Study Assessments and Procedures**

After obtaining informed consent, screening assessments will be completed to determine the patient's eligibility for enrollment. Screening assessments must be completed within 14 days prior to the first dose of investigational product. Screening assessments performed within 72 hours of the first treatment period may also be used as Day 1 assessments. The archived tumor biopsy obtained for diagnosis of this incidence of breast cancer must be available and shipped to a GSK Central lab for biomarker studies. Patients will receive study medication for a minimum of 9 days and continue treatment until scheduled surgical resection of the tumor (subjects must continue lapatinib treatment so that no more than 24 hours have elapsed between last dose and surgical resection). Surgical resection will coincide with the lapatinib trough concentration. The resected tumor tissue is required for biomarker and lapatinib intratumoral concentration analyses. A 2mL blood sample will be obtained at the time of tumor resection to examine steady state, trough plasma lapatinib concentrations. Safety (AEs, clinical laboratory values) will be assessed throughout the study.

Blood samples (2 x 5 ml tubes) will be obtained on Day 1, on the same day as the tumor resection and at the post-treatment safety visit to evaluate changes in circulating/secreted proteins (proteomic analysis) and biomarkers that may correlate with biological response at the tumor site and therefore provide an easily obtainable surrogate marker for determining therapeutic benefit of lapatinib.

A complete list of required study procedures is included in Section 14.1, Appendix 1.

# Investigational Product(s)

Patients will receive oral tablets of lapatinib ditosylate salt. Lapatinib will be supplied to the study site as 250 mg tablets. The number of tablets supplied to the patient will be dependent on the period of time between enrollment and scheduled resection.

19

### 1. INTRODUCTION

# 1.1. Background

Advances in the understanding of the basic mechanisms driving tumor growth have implicated aberrant activation of growth factor receptors as important in many types of cancer. Overexpression of ErbB2 and epidermal growth factor receptor (EGFR, ErbB1) occurs in a significant percentage of cases in many epithelial tumors. Overexpression of either receptor is often correlated with a poor patient prognosis, including reduced overall survival.

ErbB1 and ErbB2 are members of the Type I receptor kinase family (ErbB). Tyrosine autophosphorylation of ErbB1/ErbB2 in turn activates downstream signaling cascades that promote tumor cell growth and survival. Overexpression of ErbB-family members in cells *in vitro* causes transformation, such that the cells will grow in the absence of growth factors and in anchorage-independent conditions. Cells with inactive Type I receptors do not have these properties. Inhibitors of ErbB kinases have been shown to block growth and survival signals resulting in tumor cell growth arrest and/or apoptosis in ErbB1 or ErbB2 dependent tumor cell lines and xenografts. The experimental work to support this hypothesis is summarized below

### 1.2. Preclinical Results

# **Preclinical Pharmacodynamics**

Lapatinib is a specific, reversible dual inhibitor of ErbB1 and ErbB2 tyrosine kinases with IC50 values in an *in vitro* kinase assay of 10 and 9nM, respectively. Potent growth inhibition has been demonstrated in both *in vitro* and *in vivo* models of ErbB1 expression and/or ErbB2 overexpression. In an *in vitro* human transformed cell line (IC90 values  $\leq$  2.26 $\mu$ M or 1414ng/mL) no growth was observed up to 18 days after treatment with lapatinib. Treatment mice with established ErbB1 expressing or ErbB2 overexpressing human tumor xenografts resulted in the inhibition of phospho-ErbB1 and ErbB2 as well as inhibition of MAPK and PI3K/AKT downstream growth and survival pathways. These biological effects correlated with inhibition of tumor growth. Thus, the available data supports ErbB1 and ErbB2 receptor tyrosine kinase inhibition as the mechanism of action of lapatinib.

No evidence of overt central or peripheral effects in either rats or dogs, cardiovascular effects in rats, or respiratory effects in guinea pigs were noted following oral administration of up to 500mg/kilogram (kg) of lapatinib. Equivocal to very slight changes in mean systolic arterial pressure and mean arterial pressure were noted in beagle dogs at lapatinib doses of 150 and 500mg/kg. Thus, for cardiovascular effects, the no-observed adverse event level (NOAEL) in beagle dogs was 50mg/kg of lapatinib. Concentrations of lapatinib up to 2560ng/mL did not alter any other action potential parameters in isolated canine cardiac Purkinje fibers.

### **Preclinical Pharmacokinetics**

Pharmacokinetics were investigated following single intravenous and oral administration of 10mg/kg lapatinib in mice, rats and dogs. In each species, clearance was approximately equal to the hepatic blood flow and the volume of distribution was greater than the total body water volume. The mean oral bioavailability ranged from 28.7 to 63.2% and oral half-life of lapatinib ranged from 1.0 to 4.5 hours across aforementioned species. In rat and dog plasma, lapatinib-related material (lapatinib and its metabolites) had a longer oral half-life than parent lapatinib.

Lapatinib was highly bound (>99%) to mouse, rat, dog, rabbit, and human plasma proteins at concentrations ranging from 1 to  $100\mu M$  (581 to 57106 ng/mL). Species specific differences were observed in binding to erythrocytes; no erythrocyte binding was observed in rats, and binding to erythrocytes was low in mice and humans compared to rabbits and dogs.

Oral administration of lapatinib to male Wistar Han rats and male beagle dogs resulted in nearly quantitative excretion of radioactivity in feces; overall recovery was 90.0 and 89.9%, respectively. In bile duct cannulated male rats, 32% of the dose was recovered in the bile within 5 hours after dosing. Urinary excretion was < 1% of the oral dose in mice, rats and dogs.

Lapatinib showed no ability to induce CYP3A in a pregnane X receptor-screening assay. Preclinical *in vitro* studies using cDNA expressed human CYP450 enzymes and human liver microsomes have shown that lapatinib is metabolized predominantly by CYP3A4 and CYP3A5, and to a lesser extent by CYP2C19. Lapatinib was also shown to have inhibitory potential towards CYP3A4.

In a whole body autoradiography study in albino and pigmented male rats, high concentrations of radioactivity remained in the gastrointestinal tract throughout the first 24 hours after dosing. Despite the evidence for binding to melanin, no ophthalmic abnormalities or histologic findings were observed in the eye during the 2-week toxicity study in dogs.

# 1.3. Toxicology

No deaths were noted in either mice or rats following single oral doses of lapatinib up to 2,000 mg/kg or single intravenous doses up to 46 and 21 mg/kg, respectively. Following oral administration, reversible treatment-related changes in body weight and body weight gain (female rats only) as well as reversible gastrointestinal findings were observed. Similar degenerative and inflammatory gastrointestinal findings were noted on repeated dosing and were considered related to alterations in white blood cell count and differential as well as other hematologic parameters. Following intravenous administration, no treatment-related changes were noted.

Lapatinib was generally well tolerated when administered to rats and dogs at doses of  $\leq$  60 mg/kg/day and  $\leq$  40mg/kg/day, respectively, for up to 13 weeks. The NOAEL in rats was 60 (males) and 20 (females) mg/kg/day and in dogs was 10mg/kg/day (see Clinical

Investigator's Brochure (CIB) [GlaxoSmithKline Document Number RM2000/00481/06] for additional information).

Lapatinib was found to be non-mutagenic and non-clastogenic in a battery of bacterial and mammalian assays which include the Ames assay, Chinese hamster ovary chromosome aberration assay, human peripheral lymphocyte chromosome aberration assay and *in vivo* rat bone marrow chromosome aberration assay.

No fetal malformations occurred when lapatinib was administered to pregnant female rats or rabbits during the period of major organogenesis. At maternally toxic doses, lapatinib treatment was associated with growth retardation and developmental variations.

An impurity 3-chloro-4-((3-fluorobenzyl) oxy) aniline has been detected in the lapatinib drug substance batches. GlaxoSmithKline does not believe the presence of this impurity increases risk for patients who are receiving, have received or will receive other therapies known to be genotoxic such as chemotherapy, hormonal therapy or radiation.

Refer to the current Supplement to the Clinical Investigator's Brochure / Investigator's Brochure (CIB/IB) [GlaxoSmithKline Document Number RM2000/00481/06] additional information regarding the genotoxic impurity and the results of the completed genotoxicity studies.

### 1.4. Preliminary Results from Healthy Volunteers and Patients

Safety data from the first single-dose healthy volunteer study (EGF10001) indicated no clinically significant changes in safety labs or ECG parameters, pre- to post-treatment. Headache, diarrhea, rash on chest, and powdery taste were the only adverse events (AEs) reported in more than one subject.

Lapatinib concentrations appeared in serum after a lag time in absorption from the oral suspension doses (10 to 250 mg) administered in the first study. Time to achieve the peak serum concentration did not meaningfully differ between doses, averaging 3 to 4 hours post dose. Area under the serum concentration versus time curve (AUC $_{\infty}$ ) increased with increasing doses in a slightly more than proportional manner, especially at the lower end of the range of doses examined in this study. Geometric mean AUC ranged from 90 to 3,668 ng•h/mL, and maximum serum concentrations (Cmax) ranged from 11 to 317 ng/mL. Half-life increased slightly with increasing dose, from 6 to 9 hours over this dose range.

Safety data from the second, repeat-dose, healthy volunteer study (EGF10002) indicated no clinically significant changes in safety labs or ECG parameters, pre- and post-treatment. Four subjects had elevations in their ALT and/or AST post-dosing Day 4. Three of the four subjects were on placebo at the time and did not receive active investigational product. The most commonly reported AEs for EGF10002 were flatulence and headache. No AEs exceeded a Grade 2 toxicity grade per National Cancer Institute Common Terminology Criteria for Adverse Events (NCI-CTCAE), Version 3 [Cancer Therapy Evaluation Program, 2003].

Pharmacokinetic data from EGF10002 indicated that serum concentrations of lapatinib increased in proportion with increasing dose, following 8 days of once daily administration of doses ranging from 25 to 175 mg. Over this dose range, mean AUC (during the Day 8 dosing interval) ranged from 326 to 2976 ng•h/mL, and mean  $C_{max}$  (occurring 3 to 4 hours post-dose) ranged from 34 to 268 ng/mL. Half-life was independent of dose, averaging 7 h on Day 1, and 9 h on Day 8. Once daily dosing resulted in approximately 50% accumulation at 100 and 175 mg doses.

The efficacy and safety of lapatinib as a single agent or in combination with chemotherapy are being assessed in several clinical studies of metastatic breast cancer.

Single agent lapatinib exhibited a 6% clinical benefit response rate in a heavily pretreated population where an unmet medical need exist [GlaxoSmithKline Document Number RM2005/00018/00] (Study EGF20008). In a large, randomized, Phase III study EGF100151 [GlaxoSmithKline Document Number ZM2006/00137/00], lapatinib plus capecitabine demonstrated anti-tumor activity in patients with refractory, advanced metastatic breast cancer (MBC) who were previously treated with trastuzumab. Data from the pivotal study EGF100151 supported approval of lapatinib plus capecitabine for the treatment of patients with HER2-positive advanced or MBC who have received prior anthracycline, taxane and trastuzumab therapy [TYKERB Package Insert, 2007]. In this trial, lapatinib 1250mg once daily (QD) plus capecitabine 2000 mg/m2/day on days 1–14 every 3 weeks showed a statistically and clinically significant improvement in median time to progression of disease compared with capecitabine (2500 mg/m2/day on days 1–14 every 3 weeks) alone (hazard ratio 0.57; p=0.00013; median of 27.1 in the combination arm and 18.6 weeks in the control arm).

Refer to the the current Clinical Investigator's Brochure / Investigator's Brochure (CIB/IB) [GlaxoSmithKline Document Number RM2000/00481/06] for additional information on studies in healthy volunteers and cancer patients.

### 1.5. Rationale

Breast cancer is the most common malignancy in women in the United States. Despite a variety of hormonal, cytotoxic and biologic approaches, a significant number of tumors are resistant to currently approved treatment modalities [Ring, 2002]. There is evidence that ErbB1 and ErbB2 overexpression in breast cancers is independently associated with more aggressive tumor proliferation and a poor prognosis [Klijn, 1992; Kaptain, 2001]. ErbB1 and ErbB2 are members of the Type I family of receptor tyrosine kinases (ErbB). Tyrosine autophosphorylation of ErbB1/ErbB2 activates downstream effectors regulating cell proliferation and survival. A compound such as lapatinib that can selectively modulate the abnormal signaling pathways in ErbB1 expressing and ErbB2 overexpressing tumors is an alternative therapeutic approach in treating breast cancer. Although the efficacy of short-term treatment with lapatinib prior to surgical resection in breast cancer is unknown at this time, tumor biomarker data generated from this study will guide the design of future Phase II/III breast cancer efficacy trials and biomarker studies.

Trastuzumab, a humanized monoclonal antibody targeting ErbB2, is effective in treating patients whose breast cancer overexpress ErbB2 and/or display ErbB2 gene amplification, and hence, demonstrates the clinical utility of ErbB2 targeted therapy. Lapatinib, a reversible inhibitor of both ErbB1 and ErbB2 tyrosine kinases has been shown to induce growth arrest and/or tumor cell apoptosis in ErbB1 or ErbB2 dependent tumor cell lines or xenografts. The dual inhibitory nature of lapatinib offers a potential therapeutic advantage over a compound that inhibits only one tyrosine receptor kinase.

This study will examine the effect of lapatinib treatment on inhibiting ErbB1, ErbB2 and downstream signaling pathways (e.g., ERK1/2 and AKT); as well as evaluate its effect on other mediators of tumor cell growth and survival in tumor tissue from treatment-naïve breast cancer patients. Patients will receive 1500mg of lapatinib treatment daily for at least 9 days or longer and continue treatment until no more than 24 hours have elapsed prior to surgical resection of the tumor. Biomarker analyses will be performed on tumor tissue obtained pre-treatment (archived tumor tissue which is required for entry into the study) and compared with those biomarkers derived from the tissue obtained by resection post-treatment. In addition, intratumoral drug concentrations of lapatinib will be evaluated in the tumor tissue obtained at the time of resection.

# 2. OBJECTIVE(S)

# 2.1. Primary

• To investigate the effects of lapatinib on its target (ErbB1 and ErbB2) and mediators that regulate tumor cell growth and survival pathways (e.g., ERK1/2, AKT and other downstream pathways regulated by ErbB receptor signaling) through the analysis and comparison of biomarkers derived from pre-treatment and post-treatment breast tumor tissue samples.

# 2.2. Secondary

- To assess the safety and tolerability of lapatinib when administered to patients with treatment-naïve breast tumors.
- To examine the steady state, trough plasma and intratumoral concentrations of lapatinib obtained at the time of tumor resection.
- To assess the effects of lapatinib therapy on the proteomic profile in peripheral blood.
- Pharmacogenetics may be investigated if at any time it appears that there is a potential unexpected or unexplained variation in lapatinib response or handling (e.g., safety and/or clinical activity) in this clinical study or in a series of clinical studies using lapatinib.

# 3. ENDPOINT(S)

### 3.1. Primary

• Comparison of the effects of lapatinib on biomarkers involved in regulating tumor cell proliferation and survival (e.g., ErbB2, ERK1/2, AKT, and other downstream pathways regulated by ErbB receptor signaling) in pre-treatment and post-treatment breast tumor tissue samples.

# 3.2. Secondary

- Evaluation of adverse events (AEs) and changes in laboratory values from pre-dose and post-dose values.
- Examination of plasma and intratumoral lapatinib steady state trough concentrations.
- Assessment of peripheral blood to examine the proteomic profile in response to lapatinib.

### 4. STUDY DESIGN

This will be a single arm, open-label phase I study. Patients will receive 1500mg of lapatinib administered daily for a minimum of 9 days and continue treatment until surgical resection (≤24 hours).

Prior to entering the study, the documented ErbB2 status will be required for each patient. Only patients with treatment-naïve, ErbB2 positive, as defined by either overexpression of ErbB2 (3+) by semi-quantitative IHC or amplification of the ErbB2 gene by fluorescence in situ hybridization (FISH), breast tumors measuring 1 cm or greater will be eligible for the study. For eligible patients, archived tumor tissue obtained at diagnosis will represent the pre-treatment biopsy and be required for entry into the study. The pre-treatment biopsy tissue will be examined using technologies for measuring biomarkers involved in regulating tumor cell proliferation and survival (e.g., ErbB2, ERK1/2, AKT, and other downstream pathways regulated by ErbB receptor signaling). Patients will receive treatment with lapatinib for a minimum of 9 days and continue treatment until 24 hours prior to surgical resection. Patients will have their post-treatment surgical resection performed within 24 hours of last lapatinib dose. Tumor tissue obtained at resection will be examined for biomarkers as described above and compared with the results from the pre-treatment biopsy. In addition, tumor obtained at the time of resection will be examined for steady state, trough concentrations of lapatinib.

Detailed instructions on processing and shipping archived and resected tissue are included in the SRM.

Safety (AEs, clinical laboratory values) will be assessed throughout the study.

### 5. STUDY POPULATION

Female patients 18 years or older who are amenable to treatment with oral lapatinib and who will receive adjuvant chemotherapy, hormonal therapy or radiation therapy will be enrolled. An evaluable patient must meet all inclusion and exclusion criteria as detailed in Section 5.2 including taking all study medication. In addition, patients must have predose and post-dose tumor tissue samples adequate for biomarker analysis. A GSK medical monitor must approve any deviation from these criteria.

# 5.1. Number of Subjects

A sufficient number of patients will be enrolled to obtain approximately 20 evaluable patients approximately 16 study centers. Evaluable subjects are defined as those subjects whose pre-treatment tumors are determined by a central laboratory to be ErbB2 positive, which is defined as either IHC 3+ or FISH amplified. Patients must have pre-dose and post-dose tumor tissue samples adequate for biomarker analyses, and have completed lapatinib treatment for a minimum of 9 days. In addition, the elapsed time between last lapatinib dose and surgical resection must be within 24 hours.

# 5.2. Eligibility Criteria

### 5.2.1. Inclusion Criteria

A subject will be eligible for inclusion in this study only if all of the following criteria apply:

- 1. Has a histologically confirmed, treatment-naïve, breast tumor measuring 1 cm or greater.
- 2. Is Female and at least 18 years of age.
- 3. Has tumor that overexpresses ErbB2 defined by local laboratory as either:
  - 3+ by IHC

OR

- c-erbB2 gene amplification by FISH
- 1+, 2+ by IHC and c-erbB2 gene amplification by FISH.
- 4. Will receive adjuvant chemotherapy, hormonal therapy or radiation therapy
- 5. Is eligible to participate in the study if she is of:
- a. Non-child-bearing potential (i.e. physiologically incapable of becoming pregnant), including any female who:
  - Has had a hysterectomy
  - Has had a bilateral oophrectomy (ovariectomy)
  - Has had a bilateral tubal ligation, or

- Is post-menopausal (a demonstration of total cessation of menses for  $\geq 1$  year)
- b. Childbearing potential, has a negative serum pregnancy test at Screening and agrees to one of the following where considered acceptable by the institution IEC or IRB:
  - Complete abstinence form sexual intercourse from 2 weeks prior to administration of the study drug, throughout the active study treatment period, and through the follow-up visit (to occur 28 days after last dose of study medication).
  - Barrier contraception (condom with spermicidal jelly, foam suppository, or film; diaphragm with spermicide; or male condom and diaphragm).
  - Male partner who is who is sterile prior to the female subject's entry and is the sole sexual partner for that female subject.
  - Implants of levonorgesterol.
  - Injectable progestogen.
  - Any intrauterine device (IUD) with a documented failure rate of less than 1% per year.
  - Oral contraceptives (either combined or progetogen only).
- 6. Is able to swallow and retain oral medication.
- 7. Has a Karnofsky Performance Status  $\geq$  70.
- 8. Has provided written informed consent.
- 9. Hemoglobin  $\geq$  9 gm/dL
- 10. Absolute granulocyte count  $\geq 1,500/\text{mm}3 \text{ (1.5 x } 10^9/\text{L)}$
- 11. Platelet count  $\geq 100,000/\text{mm}3 (100 \text{ x } 10^9/\text{L}).$
- 12. Serum Creatinine  $\leq 3 \text{ mg/dL}$ .
- 13. Total bilirubin  $\leq 1.5 \text{mg/dL}$ .

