# 6.2. Screening Visit

Screening assessments will be completed within 14 days prior to the first dose of study drug. Screening assessments completed within 72 hours of first dose can be used as Day 1 assessments. After consent has been obtained, patients will be required to undergo a medical screen to determine whether they are eligible to participate in the study according to the criteria listed in Section 5.2. Additionally, evaluations at the Screening visit will include:

- Full physical examination, including vital signs (blood pressure and heart rate).
- Medical history including date of diagnosis of current incidence of breast cancer, histology and current sites of disease.
- Medication history
- 12-lead ECG.
- MUGA or ECHO.
- Hematology (Section 14.2, Appendix 2).
- Clinical Chemistry including serum pregnancy test for women of childbearing potential (Section 14.2, Appendix 2).

All required information will be captured in the patient source records and documented in the CRF. Any results falling outside of the normal ranges may be repeated at the discretion of the PI.

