# 6.3. On Study Assessments

On Day 1 and on the day prior to surgical resection patients will have safety, pharmacokinetic and pharmacodynamic assessments performed. The following procedures will be completed and time and date of each assessment will be documented in the source records and the CRF.

- Full physical examination, including vital signs (blood pressure and heart rate) to occur at Day 1 (if greater than 14 days since screening physical exam) and prior to scheduled surgical resection.
- Clinical Chemistry on Day 1 (if greater than 14 days since screening chemistries) and prior to scheduled surgical resection.
- Hematology on Day 1 (if greater than 14 days since screening hematology) and prior to scheduled surgical resection.

- A blood sample for pharmacokinetic analysis will be collected pre-dose on Day 1 and at the time of surgical resection. Refer to Section 6.6 for sampling schedule.
- Pharmacodynamic sampling (1 x 5 mL tubes of whole blood) on Day 1 and the on the day prior to scheduled resection. Refer to Section 6.7 for sampling schedule.
- Pharmacogenetic sampling (1 x 10 mL tube of whole blood) on Day 1 or at any time during the conduct of the study. Refer to Section 6.8 for sampling schedule.
- Assessment of study medication compliance when study medication bottle is returned prior to surgical resection.
- Assessment of adverse events continuously.
- Tumor surgical resection (≥Day 10).

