### 6.5.1.1. Pregnancy testing

All women of child-bearing potential will have a serum  $\beta$ -hCG test performed at screening.

As positive serum  $\beta$ -hCG test result at screening will exclude the patient from participation in the study (See Section 5.2).

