### 6.5.2. Clinical Laboratory Tests

Blood will be obtained for clinical laboratory tests prior to dosing on Days 1 and the day prior to surgical resection.

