#### Other Chemistries

Serum β-hCG (all women)

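### No section expressly requires a pregnancy test shortly before the first dose; the only dated serum β-hCG is at screening and may be 14 days old when dosing starts

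*Supplement*

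**What the plan says.** Three places in the current protocol (Amendment 03) deal with pregnancy testing before treatment, and all three point to screening.

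- **Section 5.2.1, no. 5b**, repeated in the Protocol Summary: "Childbearing potential, has a negative serum pregnancy test at Screening and agrees to one of the following", followed by a list of contraceptive options.
- **Section 6.2** includes the serum pregnancy test in the screening chemistry and sets the window: "Screening assessments will be completed within 14 days prior to the first dose of study drug".
- **Section 6.5.1.1**, the section on pregnancy testing, has the serum β-hCG "test performed at screening" and names no other time.

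Four places deal with Day 1 laboratory work in general.

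- **Section 6.2**: "Screening assessments completed within 72 hours of first dose can be used as Day 1 assessments".
- **Section 6.3**: "Clinical Chemistry on Day 1 (if greater than 14 days since screening chemistries) and prior to scheduled surgical resection".
- **Section 6.5.2**: "Blood will be obtained for clinical laboratory tests prior to dosing on Days 1 and the day prior to surgical resection".
- **Appendix 1**: the Clinical Labs row is marked for pre-study, Day 10 until resection, and post-study. Its Day 1 cell is empty. Footnote c to that row says pregnancy testing is required in women of child-bearing potential but gives no time.

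Appendix 2 lists "Serum β-hCG (all women") under a heading separate from Clinical Chemistry, also with no time point.

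**The concern.** Exclusion criterion 3 bars pregnant women, and Section 6.5.1.2 stops the drug at once if a β-hCG is positive after dosing has begun. The protocol thus treats pregnancy as a reason not to give lapatinib. The evidence behind that exclusion may nevertheless be two weeks old when the first dose is given, and Section 6.5.1.1 schedules no later test that could trigger the stop.

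The protocol does make dosing depend on a result elsewhere: Appendix 1 footnote a requires the local ErbB2 result before Day 1 dosing. There is no matching sentence for β-hCG. Section 7.6 holds the first dose until the pre-dose safety assessments are complete, but that helps only if β-hCG is clearly one of them.

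At stake is a pregnancy that becomes detectable between the screening test and Day 1 and is then exposed to the drug. Section 1.3 reports no malformations in rats or rabbits, and growth retardation and developmental variations at maternally toxic doses. That supports a precaution, not a claim of demonstrated harm.

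**Working it through.** The plan states no figure on this point, so the check sets the sections side by side and counts days and doses.

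**1. Maximum age of the dated test.** Section 6.2 allows screening up to 14 days before the first dose (two weeks in Appendix 1 footnote a). The only expressly dated β-hCG can therefore be 14 days old at the first dose.

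**2. Does Section 6.3 force a repeat?** Its condition is an interval greater than 14 days since the screening chemistries. For a patient screened as Section 6.2 requires, the interval is at most 14 days, and 14 > 14 is false. The condition applies only to a patient already outside the window. In addition, Section 6.2 names the pregnancy test as part of screening chemistry, while Section 6.3 says only chemistry.

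**3. Does Appendix 1 force a repeat?** No. The row that carries the pregnancy-testing footnote is blank on Day 1.

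**4. Does the 72-hour rule force a repeat?** No. It says when a screening result may stand in for a Day 1 assessment. It does not say that β-hCG is a Day 1 assessment.

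**5. Does Section 6.5.2 force a repeat?** Only in two steps: it orders laboratory blood before dosing on Day 1, and Appendix 2 lists β-hCG among the laboratory assessments. A site that combines the two draws a Day 1 β-hCG. Neither text says so, and Section 6.5.1.1 does not either.

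**6. Doses given without a further test.** Section 6.3 puts surgery at Day 10 or later ("Tumor surgical resection (≥Day 10")). Appendix 1 footnote e has daily dosing from Day 1 to the day before resection.

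- Following Section 6.5.1.1 alone: resection on Day 10, last dose on Day 9, so 9 doses. Later surgery means more, and no maximum duration is stated.
- Reading Section 6.5.2 with Appendix 2 as a Day 1 pre-dose β-hCG: 0 doses before the repeat.

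**7. Effect of a 72-hour limit.** 72 / 24 = 3 days, so the maximum age falls by 14 − 3 = 11 days. The gain is nil at sites already on the second reading.

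**8. Extra assays.** The documents do not give the share of women of child-bearing potential. Assuming 20% to 50%, the most that could be added per 20 patients is 0.20 × 20 = 4 to 0.50 × 20 = 10. Women screened within 72 hours of dosing need none.

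**The case against.** The strongest case against is that a single screening test looks intended. The Amendment 03 log records that Day 1 and follow-up tests were taken out of Section 6.5.1.1, and 5b, 6.2 and 6.5.1.1 agree with one another. Safeguards remain: exclusion 3, agreement to contraception as a condition of entry, immediate stopping on a positive test (6.5.1.2), and pregnancy reporting with outcome follow-up (6.5.1). Section 6.3 also uses 14 days, not 72 hours, as its limit for repeating examinations and laboratory work. All of this is fair. It shows that the interval was probably chosen, but does not make a two-week-old negative more informative at the first dose.

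Three stronger readings are tempting, and the documents support none of them.

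- A reader might infer that the sections contradict each other on a Day 1 pregnancy test. They do not: none names one. Sections 6.3 and 6.5.2 and Appendix 1 differ on clinical laboratory work in general, and β-hCG comes in only through footnote c and Appendix 2.
- A reader might take only the pre-resection draw from Section 6.5.2 and count the doses before it. That is not a coherent reading, because the same sentence also orders a Day 1 draw.
- A reader might add that several contraceptive options in 5b state no start or end. That is a separate drafting matter. The case for a pre-dose test does not rest on it, and the test does not need it resolved.

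**Conclusion.** The point holds as a gap in express wording. A site that follows the pregnancy-specific sections complies with the protocol while giving the first dose on a negative β-hCG up to 14 days old, and 9 or more doses in all without another test. A site that reads Section 6.5.2 with Appendix 2 as a Day 1 β-hCG has no gap. With about 16 centers for about 20 evaluable patients, a uniform reading cannot be assumed.

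The 14-day and 9-dose figures follow directly from the protocol. The number of pregnancies that a later test would find cannot be estimated, since the documents give neither the share of women of child-bearing potential nor a chance of conception. The 4 to 10 assays rest on the assumed 20% to 50% share and measure cost, not benefit.

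The change should be made because it is cheap and makes an existing exclusion enforceable at the time of dosing. No estimate, interval or analysis population is affected.

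**What to change.** Set one rule in the controlling sections and align the rest.

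- **5.2.1 no. 5b and the Summary**: require a negative serum β-hCG at screening and within 72 hours before the first dose. The screening test counts for both if taken in that time.
- **6.5.1.1**: in women of child-bearing potential, if the screening β-hCG is more than 72 hours old at the first dose, repeat it on Day 1 before dosing and give the first dose only after a negative result.
- **6.3**: add a Day 1 item with the same condition.
- **6.5.2**: state that Day 1 pregnancy testing follows Section 6.5.1.1.
- **Appendix 1 footnote c and Appendix 2**: give the same time points and population. Appendix 2 now says all women, whereas 6.2, 6.5.1.1 and footnote c limit testing to women of child-bearing potential.

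The 72 hours is the limit Section 6.2 already sets for letting screening results serve as Day 1 results.

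The cost is wording in seven places, at most one extra serum assay per woman of child-bearing potential, and a short wait for the result. Blood is already drawn before dosing on Day 1 for pharmacokinetics and proteomics (6.6, 6.7), and Section 7.6 already holds the first dose for pre-dose safety assessments, so no visit is added. A very recent conception may still be missed.
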